# 14.3.12.2 Vital signs and physical examination

For vital signs (resting blood pressure, pulse, and body temperature), the absolute values at baseline and Week 16 as well as the change from baseline to Week 16 will be summarised for each treatment group.

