Subject assessments of effica	acy and healt	h-relat	ted qua	lity of	life – d	uring t	trial vis	sits					
PGI-S 		X		X	X	X		X	X				11.7.1.2
PGI-C 				X	X	X		X	X				11.7.1.3
HEIS		X	X	X	X	X	X	X	X				11.7.1.4
PaGA		X	X	X	X	X	X	X	X				11.7.1.5

Trial ID: LP0133-1402

THIS DOCUMENT CONTAINS CONFIDENTIAL INFORMATION AND MUST NOT BE COPIED OR MADE AVAILABLE TO ANY THIRD PARTY WITHOUT THE PRIOR WRITTEN CONSENT OF THE LEO PHARMA GROUP

 Trial ID: LP0133-1402
 Date: 20-Aug-2021
 Version: 4.0, Final

 Page 27 of 157

	Screening		Ti	reatme	nt peri	od		End of treatment   Early termination, if applicable   8 (9)	Follow-up 	Primary	Unscheduled	References	
Visit	1	2	3	4	5	6	7		(9)	10	endpoint visit at	visit, if applicable 	(protocol
Week	-4 to -1	0	1	2	4	8	12	16	-	184	Week 16, if		section)
Day	-28  to -7	1	8	15	29	57	85	113	-	1274	applicable 		
Visit window (days) 	-	-	±3	±3	±3	±3	±3	±3	-	±3			
DLQI		X	X		X	X	X	X	X		X		11.7.1.6
EQ-5D-5L		X	X		X	X	X	X	X				11.7.1.7
WPAI:CHE		X			X	X		X	X				11.7.1.8
Subject assessment of safety	7												
Subject assessment of local tolerability				Wee	kly 			X	X				11.5.5
Investigator assessments of	safety												
Vital signs	X	X						X	X			(X)	11.5.1
Physical examination	X							X	X			(X)	11.5.2
ECG	X		X					X	X			(X)	11.5.3
Chemistry, haematology (central laboratory) 	X	X		X	X	X	X	X	X			(X)	11.5.4
Serology, total IgE (central laboratory)	X												11.5.4
Urine pregnancy test 	X	X			X	X	X	X	X			(X)	11.5.4
Urinalysis (urine dipstick) 	X	X		X	X	X	X	X	X			(X)	11.5.4
Investigator assessment of local tolerability			X	X	X	X	X	X	X			(X)	11.5.5

Date: 20-Aug-2021 Version: 4.0, Final

Page 28 of 157

	Screening 1	Treatment period							Early termination, if applicable 	Follow-up 	Primary endpoint	Unscheduled	References
Visit		2	3	4	5	6	7	8	(9)	10	visit at Week 16, if applicable 	visit, if applicable 	(protocol section)
Week	-4 to -1	0	1	2	4	8	12	16	-	18 			
Day	-28  to -7	1	8	15	29	57	85	113	-	1274			
Visit window (days) 	-	ı	±3	±3	±3	±3	±3	±3	-	±3			
Scoring of suspected local skin reaction related to IMP (if applicable) 			(X)	(X)	(X)	(X)	(X)	(X)	(X)			(X)	11.5.5
IMP patch test (if applicable) 			(X)	(X)	(X)	(X)	(X)	(X)	(X)			(X)	11.5.5.1
AEs	X	X	X	X	X	X	X	X	X	X	X	X	13

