Other assessments													
New CHE lesions			X	X	X	X	X	X	X	X	X	(X)	9.2, 11.2.6
PK blood sample 			X		X			X	X				11.6
Photography of the whole hands, including wrists (selected trial sites) 		X			X	X		X	X			(X)	11.7.2
Return of eDiary (if applicable)								X 	$X^{26}$		X		11.3
End of treatment/trial													
End-of-treatment form								X	X				11.8
End-of-trial form 								X	X	X	X	(X)	11.8

 End-of-treatment assessments will be conducted at Week 16. For subjects who participate in the LTE trial (LP0133-1403), the Week 16 visit in the present trial will coincide with the baseline visit in the LTE trial.

 Subjects who discontinue IMP prior to Week 16 or withdraw from trial will be asked to return to the trial site for an early termination visit as soon as possible after the last IMP application for completion of all trial procedures scheduled for the visit at Week 16. Subjects who discontinue IMP will also be asked to return at Week 16 (see footnote 5).

Trial ID: LP0133-1402

THIS DOCUMENT CONTAINS CONFIDENTIAL INFORMATION AND MUST NOT BE COPIED OR MADE AVAILABLE TO ANY THIRD PARTY WITHOUT THE PRIOR WRITTEN CONSENT OF THE LEO PHARMA GROUP

- 3) All subjects not participating in the LTE trial will be asked to attend a follow-up visit (performed via phone, but can be a site visit if needed) approximately 2 weeks after the last IMP application for assessment of safety. Subjects who will participate in the LTE trial will not be required to complete the safety follow-up period, as collection of safety data and safety surveillance will continue in the LTE trial.
- 4) As the follow-up visit will be scheduled approximately 2 weeks after the last IMP application, the follow-up visit can occur before Week 18/Day 127 for subjects who discontinue IMP prior to Week 16.
- 5) Subjects who discontinue IMP treatment prior to Week 16 will be asked to return to the trial site at Week 16 (scheduled 112 days after baseline) for a primary endpoint visit.
- 6) Unscheduled visits occur if subjects need to make a visit in between the scheduled visit dates, e.g. due to an AE or due to a significant change in their disease state. Assessments to be performed at unscheduled visits will be at the discretion of the investigator.

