## 11.8 End of trial

### **End-of-treatment form**

An end-of-treatment form will be completed in the eCRF for all randomised subjects exposed to IMP when they have had their last application of IMP. This form will also be completed for subjects who permanently discontinue IMP prior to Week 16 and subjects who withdraw from trial, unless they were never exposed to IMP (see Section 10.3 for early termination assessments).

The date of last application of IMP will be recorded on the end-of-treatment form. It will also be recorded if the subject completed the treatment (i.e. did not discontinue IMP prior to the Week 16 visit) and, if not, whether the reason for not completing the treatment period was related to COVID-19. If the subject did not complete the treatment, the primary reason for permanent discontinuation of IMP must be recorded (see Section 10.2).

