# 14.2 Trial analysis sets

All screened subjects will be accounted for in the CTR.

All subjects randomised and exposed to IMP will be included in the FAS and will be analysed based on the randomised treatment allocation. Exclusions from the FAS can be considered in special cases as described in ICH E9, Section 5.2.1, Full Analysis Set. If it is decided to exclude a subject from the FAS, a justification addressing ICH E9 will be given.

A safety analysis set will be defined as all subjects exposed to IMP.

The decisions regarding inclusion/exclusion of subjects or subject data from the trial analysis sets will be documented in the analysis set definition document before breaking the randomisation code.

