# 14.3.12.3 Clinical laboratory evaluation

For laboratory parameters, the absolute values as well as the changes from baseline will be summarised by visit for each treatment group.

A shift table will be produced for relevant parameters showing the categories at baseline against those at end of treatment (Week 16).

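### The only numerical vital-sign summary is fixed at Week 16, so it omits the one post-baseline set scheduled for subjects who stop IMP early, taken at early termination

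*Combined protocol and SAP*

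**What the plan says.** Section 14.3.12.2 contains one planned display. It covers blood pressure, pulse and temperature, and the plan is that "the absolute values at baseline and Week 16 as well as the change from baseline to Week 16 will be summarised for each treatment group". No other numerical summary of vital signs is planned. Section 14.3.12 bases safety analyses on the safety analysis set, and Section 14.2 fixes who is in it: "A safety analysis set will be defined as all subjects exposed to IMP".

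For laboratory data, Section 14.3.12.3 plans summaries of values and changes at each visit, and in addition: "A shift table will be produced for relevant parameters showing the categories at baseline against those at end of treatment (Week 16".

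The visit structure is in Section 4, Panel 2. Footnote 1 says: "End-of-treatment assessments will be conducted at Week 16". Footnote 2 asks subjects who stop IMP or withdraw to attend a separate early termination visit (Visit 9), soon after their last application, "for completion of all trial procedures scheduled for the visit at Week 16". Footnote 5 adds a later visit for efficacy: "Subjects who discontinue IMP treatment prior to Week 16 will be asked to return to the trial site at Week 16". Section 11.8 says of the end-of-treatment form: "This form will also be completed for subjects who permanently discontinue IMP prior to Week 16".

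**The concern.** The analysis text names Week 16, but for an early stopper the schedule places the last vital signs at a different visit. If the text is followed, the post-baseline part of the vital-sign table describes only subjects assessed at the Week 16 end-of-treatment visit, who are essentially those who completed treatment.

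The omitted group is unlikely to be a random subset. Section 10.2 requires IMP to be stopped for certain adverse events, rescue treatment, a positive IMP patch test and defined liver-test abnormalities. Section 5.3 regards stopping and rescue as mostly reflecting poor efficacy or unacceptable treatment features. A safety display selected towards completers is weaker evidence about all exposed subjects, and the loss could differ between arms. The measurements are already scheduled, so what is missing is a rule for using them.

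**Working it through.** The plan gives no figure to reproduce here. The check sets the schedule beside the analysis text.

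1. Post-baseline entries in Panel 2, read column by column:

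| Row | Weeks 1–12 | Week 16 (Visit 8) | Early termination (Visit 9) | Follow-up | Primary endpoint visit | Unscheduled |
|---|---|---|---|---|---|---|
| Vital signs | none | X | X | none | none | (X) |
| Chemistry, haematology | Weeks 2, 4, 8, 12 | X | X | none | none | (X) |
| End-of-treatment form | none | X | X | none | none | none |

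The IGA-CHE row does carry an X under the primary endpoint visit, so the blank for vital signs is not a shifted column.

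2. Scheduled post-baseline vital-sign sets used by the Section 14.3.12.2 summary:
- Completer: one set (Visit 8), and 1 of 1 is used.
- Early stopper: one set (Visit 9), and 0 of 1 is used, even if the subject returns at Week 16 as asked.

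3. Is there a rule elsewhere that carries Visit 9 into the summary? Section 14.3.14 makes by-visit tables observed-case and maps no visit to another. Section 14.3.15 refers missing values to Section 14.3.6, which deals with efficacy and quality-of-life endpoints on the FAS. Panel 23 sets out the handling of early stoppers' data in detail for those endpoints; nothing similar covers vital signs.

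4. Laboratory data differ because there is also a by-visit summary. Counting scheduled samples plus the early termination sample, that summary retains:
- stop before Week 2: 0 of 0 + 1 = 1;
- Weeks 2–4: 1 of 1 + 1 = 2;
- Weeks 4–8: 2 of 2 + 1 = 3;
- Weeks 8–12: 3 of 3 + 1 = 4;
- Weeks 12–16: 4 of 4 + 1 = 5.

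If Visit 9 is tabulated as a visit, all of them are retained. Only the shift table is in question. Its bracketed Week 16 and footnote 1 point to Visit 8 alone. The end-of-treatment form at both visits and footnote 2 allow early termination to count as end of treatment. The text does not choose.

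5. Illustrative size, with the discontinuation rate assumed because none is given:
- 450 × 0.05 = 22.5 and 450 × 0.20 = 90 subjects without a post-baseline value in the vital-sign summary;
- 450 − 22.5 = 427.5 and 450 − 90 = 360 remaining at most.

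Attendance at Visit 9 is only requested (Section 10.3) and some subjects will be lost to follow-up (Section 10.4), so 23 to 90 is an upper bound on those recoverable. Assuming 50% to 100% attend, the range is 22.5 × 0.50 = 11.25 to 90 × 1.00 = 90. The base of 450 is subjects randomised; the safety set is those exposed and may be slightly smaller.

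**The case against.** The best case for the plan has four parts.

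- **A fixed-time summary is legitimate.** Every Week 16 value has about the same time on treatment, which an end-of-treatment value does not. This stands, and it is why the Week 16 table should stay.
- **Detail is deferred.** Section 14.3.14 says a statistical analysis plan will be finalised before unblinding, and visit mapping for descriptive tables is often settled there. That makes the point easy to fix. It does not remove it, because the current text states a rule, and following that rule leaves these values out.
- **Adverse-event reporting covers what matters.** Section 11.5.1 has clinically significant new findings or deterioration reported as AEs, and Section 14.3.12.1 tabulates and lists AEs leading to discontinuation. This limits the consequence considerably. It does not replace a between-arm numerical summary, since changes judged not clinically significant never become AEs.
- **The exclusion is not total.** Early stoppers still contribute baseline values. An early termination visit just before Day 113 could also fall inside the ±3-day window of Visit 8, and the text does not say how it would be labelled.

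A reader might infer that the laboratory shift table also excludes early stoppers. The documents do not establish that: the wording is ambiguous, and these subjects' earlier laboratory values are in the by-visit summaries in any case.

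**Conclusion.** The point holds for vital signs as a minor one. As written, early stoppers' only scheduled post-baseline vital signs do not enter the only planned numerical summary, although the safety set is all exposed subjects. The structural result (0 of 1 sets used, against 1 of 1 for completers) needs no assumption. The number of subjects is unknown; the 23 to 90 rests entirely on the assumed 5% to 20% and on 450 as the base.

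For the laboratory shift table there is an ambiguity to clear up, not an error.

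A reader might infer that the safety analysis as a whole is restricted to completers, or that the vital-sign comparison is biased in a known direction. Neither is supported. AE analyses include every exposed subject, and the documents give no discontinuation rates by arm and no vital-sign effect from which to derive a direction. Power, type I error, the efficacy analyses and the AE-based safety endpoint are unaffected.

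**What to change.** In Section 14.3.12.2 or the SAP, before unblinding, add a summary of the end-of-treatment vital-sign value and its change from baseline. Define that value as the Week 16 value or, for subjects who stop IMP early, the early termination value. Keep the Week 16 summary alongside it and report the number of subjects in each, so the reader can see how many values come from early termination.

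In Section 14.3.12.3, state that the end-of-treatment category in the shift table uses the same definition.

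The cost is a few lines of wording and one additional descriptive table; no new data are collected. The drawback is that end-of-treatment values come from differing times on treatment, which the retained Week 16 table offsets.

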# 14.3.12.3 Clinical laboratory evaluation

For laboratory parameters, the absolute values as well as the changes from baseline will be summarised by visit for each treatment group.

A shift table will be produced for relevant parameters showing the categories at baseline against those at end of treatment (Week 16).

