# 11.5.4.2 Investigator evaluation of laboratory samples

## **Central laboratory**

Chemistry, haematology, urinalysis (if applicable), and serology will be analysed by a central laboratory which will provide results to the trial sites. Laboratory parameters will be classified as 'low', 'normal', or 'high', depending on whether the value is below, within, or above the reference range, respectively. The investigator must evaluate all results outside the reference range ('clinically significant' or 'not clinically significant') and sign and date the evaluation. The signed and dated version will be filed with the investigator's trial documentation. In case of clinically significant abnormal results, appropriate action, as judged by the investigator, must be taken.

If a screening laboratory result is abnormal and clinically significant, it will be at the investigator's discretion to decide if the subject should be randomised into the trial (respecting exclusion criterion no. 20).

A laboratory manual will be provided to the trial sites specifying the procedures for collection, processing, storage, and shipment of samples, as well as laboratory contact information specific to this trial.

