### Reporting in eCRF

At each visit, the site staff will record in the eCRF if a blood sample was taken. If not, a reason should be provided. The investigator's assessment of the results ('normal', 'abnormal, not clinically significant', 'abnormal, clinically significant') will be recorded in the eCRF.

It will be recorded in the eCRF if a urine dipstick test was performed and whether urinalysis is required for further assessment, as judged by the investigator. If so, a urine sample should be sent to the central laboratory. If the urine sample was not tested with a dipstick, a reason will be provided. The investigator's assessment of the urine dipstick results ('normal', 'abnormal') will be recorded in the eCRF. In case urinalysis is performed, the investigator's

assessment of the results ('normal', 'abnormal, not clinically significant', 'abnormal, clinically significant') will be recorded in the eCRF.

It will be recorded in the eCRF if the subject is a woman of childbearing potential and if a urine pregnancy test was performed. If not, a reason should be provided. Also, the date and the outcome of the urine pregnancy test will be recorded in the eCRF ('positive', 'negative').

Clinically significant abnormal laboratory results at the screening visit will be documented as medical history in the eCRF. At subsequent visits, any clinically significant deterioration of a pre-existing condition will be reported as an AE. Any new clinically significant sign, symptom, or illness occurring after randomisation will be reported as an AE in accordance with Section 13.3.

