# 14.3.14 General principles

Significance tests, for binary and continuous endpoints, will be one-sided using the 2.5% significance level. The Gray's test, used for time-to-event endpoints, will be two-sided using a 5% significance level. All confidence intervals will be presented with 95% degree of confidence, unless otherwise specified.

An observed-cases approach will be used for tabulations of data by visit (that is, involving only those subjects who attended each specific visit).

Page 129 of 157

Categorical data will be summarised using the number and percentage of subjects in each category. Continuous data will be summarised using the mean, median, SD, 1st quartile, 3rd quartile, minimum, and maximum values.

Baseline measurements will be defined as the latest available observation at or prior to the date of randomisation.

All the analyses specified in the protocol will be reviewed in relation to the blinded data actually obtained, and the statistical analysis plan will be finalised before breaking the randomisation code.

Any changes from the statistical analyses planned in this clinical trial protocol will be described and justified in a protocol amendment, the statistical analysis plan, and/or in the CTR, dependent on the type of change.

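### The only categorical laboratory table compares baseline with Week 16, so low/high shifts at Weeks 2-12 that resolve are counted by subject only if reported as adverse events

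*Combined protocol and SAP*

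**What the plan says.** Section 14.3.12.3 (Clinical laboratory evaluation) plans two outputs. For continuous values, "the absolute values as well as the changes from baseline will be summarised by visit for each treatment group". For categories there is one shift table, limited to relevant parameters, "showing the categories at baseline against those at end of treatment (Week 16").

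Three other places matter:

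- Panel 2 (section 4) schedules central chemistry and haematology at screening, at baseline, at Weeks 2, 4, 8, 12 and 16, and at early termination, with optional unscheduled samples.
- Section 11.5.4.2 sets the categories: "Laboratory parameters will be classified as 'low', 'normal', or 'high', depending on whether the value is below, within, or above the reference range".
- The eCRF reporting text of section 11.5.4 adds a second grading: "The investigator's assessment of the results ('normal', 'abnormal, not clinically significant', 'abnormal, clinically significant') will be recorded in the eCRF". Section 14.3.12.3 plans no table of that grading.

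The statistics for the by-visit summaries come from section 14.3.14: "Continuous data will be summarised using the mean, median, SD", together with quartiles, minimum and maximum. No count of subjects outside the reference range is listed.

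**The concern.** The trial draws five scheduled post-baseline samples per subject, and every value can be classed against the reference range. The category table uses one of the five. A completer who is normal at baseline, low at Week 4 and normal at Week 16 sits in the normal-to-normal cell, alongside subjects who never left the range.

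Evaluating safety against vehicle is a stated secondary objective (Panel 4). Section 5.5 argues that the systemic risks of the JAK-inhibitor class are not relevant here because systemic exposure is very low. A count by arm of subjects whose laboratory values left the range at any time on treatment would be direct evidence on that argument. A Week 16 comparison is weaker evidence, because an empty off-diagonal could mean either no effect or an effect that came and went.

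**Working it through.** The plan states no figure on this point, so the check sets the schedule against the planned tables and then sizes the gap under stated assumptions.

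**Coverage of the category table.** Scheduled post-baseline samples (Panel 2): Weeks 2, 4, 8, 12 and 16, which is 5. Samples entering the shift table (14.3.12.3): Week 16, which is 1. So 5 − 1 = 4 of 5 scheduled samples enter no laboratory category table.

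**What else would register a shift at Weeks 2-12.**

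- *Adverse event tables.* Appendix 1 makes a laboratory abnormality an adverse event when the investigator considers it clinically significant. Section 14.3.12.1 counts treatment-emergent events by subject and by event. This is a count by subject, but it depends on judgement at about 55 sites (section 7.2).
- *By-visit summaries.* These describe each arm's distribution at each visit. They do not say how many subjects were outside the range, or whether it was the same subject at two visits. The minimum and maximum also depend on arm size. With no drug effect and normally distributed values (assumption), the expected maximum is 2.88 SD for n = 300 and 2.65 SD for n = 150, the arm sizes from 450 subjects allocated 2:1.

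**Share of affected subjects that the Week 16 column misses.** The rates below are assumptions; none is in the documents. Take one parameter and a subject in range at baseline. Let q be the probability of going out of range at a visit when in range at the previous one, and r the probability of staying out when already out. The five visits are treated as equal steps, although their spacing is not equal.

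- P(out of range at least once) = 1 − (1 − q)^5
- P(out at Week 16) = q × (1 − (r − q)^5) / (1 − (r − q))
- P(out only before Week 16) = the first minus the second
- Share missed = P(out only before Week 16) / P(out at least once)

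With q = 0.01, P(out at least once) = 1 − 0.99^5 = 0.0490 for every r. Expected subjects missed are 300 and 150 times the fourth column.

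| Persistence r | P(out at least once) | P(out at Week 16) | P(out only before Week 16) | Share missed | Expected missed, 300 / 150 |
|---|---|---|---|---|---|
| independent (r = q) | 0.0490 | 0.0100 | 0.0390 | 80% | 11.7 / 5.9 |
| 0.25 | 0.0490 | 0.0131 | 0.0359 | 73% | 10.8 / 5.4 |
| 0.50 | 0.0490 | 0.0191 | 0.0300 | 61% | 9.0 / 4.5 |
| 0.75 | 0.0490 | 0.0299 | 0.0191 | 39% | 5.7 / 2.9 |
| 0.90 | 0.0490 | 0.0401 | 0.0089 | 18% | 2.7 / 1.3 |

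In the independent case the share hardly depends on q: it is 80% at q = 0.005 and 78% at q = 0.05. Persistence drives the result.

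**The case against.** A reader might infer that transient shifts are counted nowhere, or that the plan could not reveal a transient laboratory effect at all. The documents do not support either reading. Section 11.5.4.2 requires the investigator to evaluate every out-of-range result. One judged clinically significant becomes an adverse event and is counted by subject and arm. A transient effect shared by many subjects would also show in the by-visit change from baseline, whose mean, median and quartiles, unlike the extremes, can be compared under 2:1 allocation. What escapes is narrower: sporadic out-of-range values not judged clinically significant, and any count that does not depend on that judgement.

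Three further objections have weight.

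- The size of the gap is assumed, and the 80% figure requires independence between visits. This stands, which is why a range is given.
- Section 14.3.14 leaves the SAP to be finalised before the randomisation code is broken, so a table could still be added there. That is true, but nothing in the text provided commits to one. It makes the change easier rather than unnecessary.
- Worst-value tables pick up noise. If 5% of unaffected values fall out of range at each of five independent visits (assumption), 1 − 0.95^5 = 23% of subjects would be flagged per parameter by chance. This stands as a cost. It applies to both arms, so the vehicle percentage is the reference.

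The only secondary safety endpoint is the number of treatment-emergent adverse events per subject (Panel 4), so no endpoint and no confirmatory result depends on this table.

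**Conclusion.** The point holds as a cheap improvement to the descriptive safety analysis. Low/high shifts that appear at Weeks 2-12 and resolve by Week 16 enter no laboratory category table, and whether they are counted by subject depends on the investigator's judgement of clinical significance. That much follows from the schedule and section 14.3.12.3 without any assumption.

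The size does rest on assumptions: about 80% of subjects with any out-of-range value would be missed under independence between visits, and 73% down to 18% with persistence of 0.25 to 0.9 and a 1% onset rate per visit. The gap is therefore large for brief changes and modest for lasting ones. Sample size, alpha and power are unaffected.

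**What to change.** In section 14.3.12.3 or the SAP, keep the Week 16 shift table. Add, for the same relevant parameters and by treatment group, a shift from baseline to the worst post-baseline category, with lowest and highest shown separately. Use all scheduled and unscheduled samples after the first IMP application, up to and including the Week 16 or early termination visit.

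The window should be tied to the visit and not to the last application. Under section 9.2 the last application is made at home before the Week 16 visit, and under Panel 2 (footnote 2) the early termination visit follows the last application. A cut-off at last application, read literally, would drop both samples.

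The cost is one sentence and one extra table from data already collected. The downside is more chance abnormalities in both arms, so the table should be read as a comparison with vehicle and not as a rate in its own right.
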